3.3.1 General Study Level Definitions

3.3.1.1 Study Day and Baseline

Whenever data is summarised over time, study day will be calculated based on the actual assessment date. All data will be summarised in relation to date of first IP administration.

If actual assessment date is prior to the first IP administration, then study day will be:

Study day = Actual assessment date – first IP administration date.

If actual assessment date is on or after the first IP administration, then study day will be:

Study day = Actual assessment date - first IP administration date + 1.

In general, the last non-missing measurement prior to first application of IP will serve as the baseline measurement for efficacy and safety endpoints.

If multiple visits are equally eligible to assess patient status at baseline (for example assessments both on the same date prior to first dose of IP administration), the average (for numeric values)/worst (for categorical values) of the measurements will be taken as the baseline value. If several assessments are performed on the same day as first dose of IP administration, only those with time recorded prior to IP time of administration will be used to assess patient status at baseline (i.e. if time of assessment on the same day as IP administration is missing, the assessment will be assumed to be collected after administration).

If no value exists before the first dose of any study drug, then the baseline value will be treated as missing.

Orthostatic blood pressure measurements, even if assessed prior to IP administration, will not be used as baseline; they will be summarised and listed separately.

For daily PEF, Cough VAS Assessment and BCSS, baseline will be defined as the average from last 2 weeks (14 days) results prior to first dose of investigational product, i.e. from evening of Study Day -14 to the morning of Study Day 1. If there are fewer than 7 completed days in the 14-day baseline period (where a complete day = entry from the evening AND the following morning, i.e. one day will include all the data performed at or after 12.00 in the afternoon up to 12.00 the following morning) then baseline will be set to missing.

The baseline value of each CompEx variable will be defined as the average of all available measurements during the baseline period. There must be at least 50% of non-missing daily assessments for a variable in order for baselines to be calculated. Daily assessments could be made up of a single assessment in either the morning or evening, or two assessments daily, depending on the variable. For a baseline window of 14 days and for variables where assessments are available morning and evening, there should be at least 7 days of non-missing morning assessments and 7 days of non-missing evening assessments. For variables using once daily assessment, 7 days of non-missing assessments (from either morning or evening, depending on when the variable is captured) should be used.

The baseline cough frequency is derived from the cough monitoring performed at Visit 3 (or Revisit 3 for rescreened participants). For cough frequency, a baseline value will be defined for 24h, waking and sleeping.

For spirometry, if multiple assessments have been collected during the same day, the 'best result' flag out of all measurements per timepoint (including baseline) will be used in the analysis.

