8.2.4 Participant-Reported Outcomes

The following assessments will be performed to evaluate respiratory symptoms at the times indicated in the SoA (Table 1). Participants should complete on-site PRO assessments before all other scheduled assessments in a quiet area. The appointed site personnel should also stress that the information is confidential. Therefore, if the participant has any medical problems, he or she should discuss them with the doctor or study nurse separately from the PRO assessments.

All PROs will be completed on the e-Diary. The participant will be asked to bring the device

with the e-Diary on with them to all on-site visits.

• Exacerbations of Chronic Pulmonary Disease Tool—Patient-reported Outcome (EXACT) The EXACT is a 14-item ePRO instrument developed to assess the frequency, severity and duration of COPD exacerbations (Jones et al 2011; Leidy et al 2011). The instrument was developed for daily, at home, administration using a handheld electronic device. Respondents are instructed to complete the diary each evening just prior to bedtime and to answer the questions while considering their experiences "today". The daily EXACT total score has a range of 0 to 100 with higher scores indicative of greater severity. Total score changes are used to identify the onset and recovery from an EXACT defined exacerbation event. In identifying event onset and recovery, the EXACT can provide information on event frequency and duration as well as event severity.

The EXACT will be performed at on-site visits using the e-Diary. The EXACT questionnaire is presented in Appendix G.

• Breathlessness, Cough and Sputum Scale (BCSS)

The BCSS is a 3-item questionnaire rating breathlessness, sputum, and cough on a 5-point Likert scale from 0 (no symptoms) to 4 (severe symptoms) (Leidy et al 2003). Item scores can be reported as domains scores and are summed to yield a total score. The BCSS will be captured each evening via the e-Diary over the period indicated in the SoA (Table 1). The recall period for the BCSS is "today".

• Cough Visual Analogue Scale (Cough VAS)

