SV5	Week 12	Week 12	84	All assessments before the administration of investigational product from Day 81-Day 87

 $\overline{SV} = Study Visit.$

Daily assessments from eDiary (PEF, BCSS, cough VAS) will primarily be summarised and analysed as 2-weekly averages, separately. The assessment period of visit windows will be defined in Table 8.

Table 8 Labelling of 2-weekly periods for daily PEF, BCSS, cough VAS

2-weekly period	Adjusted defined windows visit	Scheduled day
Baseline: as defined in Section 3.3.1.1	Baseline	1
Period 1: Evening of Day 1 – Morning of Day 15	Week 2	15
Period 2: Evening of Day 15 – Morning of Day 29	Week 4	29
Period 3: Evening of Day 29 – Morning of Day 43	Week 6	43
Period 4: Evening of Day 43 – Morning of Day 57	Week 8	57
Period 5: Evening of Day 57 – Morning of Day 71	Week 10	71
Period 6: Evening of Day 71 – Morning of Day 85	Week 12	85
Period 7: Evening of Day 85 – Morning of Day 99	Week 14	99
Period 8: Evening of Day 99 – Morning of Day 113	Week 16	113
Period 9: Evening of Day 113 – Morning of Day 127	Week 18	127
Period 10: Evening of Day 127 – Morning of Day 141	Week 20	141
Period 11: Evening of Day 141 – Morning of Day 155	Week 22	155
Period 12: Evening of Day 155 – Morning of Day 172*	Week 24	169

^{*}the 2-weekly period for Period 12 is extended to "Morning of Day 172", to allow for the +3 day window.

The Early Discontinuation and unscheduled visits will be included when applying the visit windows to ensure that all available data are used in the analysis.

For 2-weekly summaries, the mean of all non-missing observations within an assigned window is calculated. If there are fewer than 7 completed days in the 14 day period (where a complete day = entry from the evening AND the following morning) then the analysis value will be set to missing.

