4.2.5 Secondary Endpoint – BCSS score

4.2.5.1 Definition

Breathlessness, Cough and Sputum Scale (BCSS) is a 3-item questionnaire rating breathlessness, sputum, and cough on a 5-point Likert scale from 0 (no symptoms) to 4 (severe symptoms). Item scores can be reported as domains scores and are summed to yield a total score. The BCSS will be captured each evening via the e-Diary. If there are repeated measurements in a day (evening), then the first measurement will be used in the analysis.

4.2.5.2 **Derivations**

Change from baseline in BCSS average score to Weeks 12 and 24 will be calculated as specified in Section 3.3.1.2.

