4.2.6 Secondary Endpoint – Cough VAS

4.2.6.1 Definition

Participants will be asked to complete a cough severity VAS (100-point linear scale marked with a horizontal or vertical line by the patient, with 0 representing "no cough" and 100 representing "worst cough") measuring subjective assessment by the patient of the prior 24 hours for severity of cough symptoms.

The Cough VAS will be completed each morning in the e-Diary until Week 24.

4.2.6.2 **Derivations**

Change from baseline in Cough VAS average score to Weeks 12 and 24 will be calculated as specified in Section 3.3.1.2.

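### The evening-plus-morning completeness rule can discard valid two-week means of BCSS (evening only) and Cough VAS (morning only)

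*SAP*

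**What the plan says.** SAP Section 3.3.1.1 gives one baseline rule for daily PEF, Cough VAS and BCSS: the mean over the 14 days before first dose, set to missing if there are "fewer than 7 completed days in the 14-day baseline period (where a complete day = entry from the evening AND the following morning"). A day runs from noon to noon.

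SAP Section 3.3.3 repeats the threshold for the post-baseline two-week periods: the value is missing if there are "fewer than 7 completed days in the 14 day period (where a complete day = entry from the evening AND the following morning"). The mean itself does not depend on pairing: "For 2-weekly summaries, the mean of all non-missing observations within an assigned window is calculated".

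The two instruments are collected once a day. For BCSS, SAP Section 4.2.5.1 states: "The BCSS will be captured each evening via the e-Diary", and Protocol Section 8.2.4 agrees: "The BCSS will be captured each evening via the e-Diary over the period indicated in the SoA". For Cough VAS, SAP Section 4.2.6.1 states: "The Cough VAS will be completed each morning in the e-Diary until Week 24". PEF is measured twice daily (Protocol Section 8.2.3).

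For the CompEx variables, Section 3.3.1.1 has a separate baseline rule that counts a once-daily variable's own entries and asks for seven. Nothing extends that rule to BCSS or Cough VAS, and nothing exempts them from the paired rule.

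**The concern.** The paired rule suits a twice-daily measurement. For a once-daily instrument, the other half of the pair is a diary session that holds no score for it. A participant can therefore supply every BCSS score in a fortnight and still have no BCSS value, because mornings were missed; the mirror case holds for Cough VAS.

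Change from baseline in both instruments at Weeks 12 and 24 is a secondary endpoint. The SAP does not impute missing efficacy data, so a discarded mean is lost at that time point. A discarded baseline removes the participant from that instrument's MMRM altogether. At stake is precision on two secondary endpoints, lost for reasons unrelated to the scores.

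The wording is also unclear, because *entry* is not defined. Read as any diary entry, the rule discards valid scores. Read as an entry of the instrument itself, neither instrument could ever have a complete day and both would always be missing. Neither reading works.

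**Working it through.** **The plan's own thresholds.** The CompEx rule asks for 50% of 14 days: 0.50 × 14 = 7. Inclusion criterion 7 asks for 70% diary compliance: 0.70 × 14 = 9.8, rounded up to 10 mornings and 10 evenings. Both reproduce.

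**Does pairing buy anything?** Seven pairs contain seven evening and seven morning entries, so the guaranteed minimum is seven BCSS or seven Cough VAS scores. Requiring seven own entries guarantees the same. In the other direction, 14 evenings with 6 mornings give at most 6 pairs, so 14 scores are dropped.

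**How many pairs are possible?** A full period has 14. The diary stops on the day of SV7 or the early discontinuation visit (Protocol Section 1.3), which shortens the last period:

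- Week 24. Period 12 starts on the evening of Day 155, so possible pairs = SV7 day − 155: 13 on Day 168, 10 on Day 165 and 16 on Day 171 (the ±3-day limits). Table 8 notes that "the 2-weekly period for Period 12 is extended to" the morning of Day 172, but that helps only if the visit is late.
- Week 12. "Period 6: Evening of Day 71 – Morning of Day 85" holds 14 pairs, but 13 if a combined SV5/SV7 (Protocol Section 7.1.4) falls on Day 84.

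**Share of periods set to missing.** Inputs:

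- p = completion rate of each diary session. This is an assumption, since the documents give no on-treatment rates. The 80% and 85% used are the adherence levels below which sites should act (Protocol Section 1.3); 90% is added for comparison.
- ρ = correlation between completing an evening and the next morning, also assumed.
- Chance that a pair is complete: q = p² + ρp(1−p). For p = 0.80 this is 0.64 (ρ = 0) or 0.72 (ρ = 0.5); for p = 0.85, 0.7225 or 0.78625; for p = 0.90, 0.81 or 0.855.
- Loss under the paired rule = P(Binomial(n, q) ≤ 6). Loss under an own-entry rule = P(Binomial(n, p) ≤ 6).

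| Possible pairs n | p | Paired, ρ = 0 | Paired, ρ = 0.5 | Own entries |
|---|---|---|---|---|
| 14 (full period) | 80% | 8.8% | 2.1% | 0.2% |
| 14 | 85% | 2.0% | 0.4% | 0.03% |
| 14 | 90% | 0.17% | 0.03% | 0.002% |
| 13 (last visit Day 84 or 168) | 80% | 14.7% | 4.4% | 0.7% |
| 13 | 85% | 4.2% | 1.0% | 0.1% |
| 13 | 90% | 0.52% | 0.10% | 0.01% |
| 10 (SV7 on Day 165) | 85% | 29.2% | 14.6% | 5.0% |
| 16 (SV7 on Day 171) | 85% | 0.4% | 0.04% | 0.002% |

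If missed mornings and evenings coincide fully, the two rules lose the same periods.

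**Effect on precision.** The ratio of standard errors, paired rule to own-entry rule, was taken from the expected generalised-least-squares information over all missing patterns, with independent loss in each period. Assumed within-patient correlations were compound symmetry 0.5 and 0.7, and AR(1) 0.8 and 0.9. Week 12 uses full periods, with participants having either 6 or 12 periods. Week 24 uses 12 periods, with n = 13 in the last.

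| p, ρ | Week 12 SE increase | Week 24 SE increase (SV7 on Day 168) |
|---|---|---|
| 80%, 0 | 0.5–2.7% | 1.7–4.4% |
| 80%, 0.5 | 0.1–0.6% | 0.4–1.1% |
| 85%, 0 | 0.1–0.6% | 0.4–1.2% |
| 85%, 0.5 | 0.1% or less | 0.1–0.3% |

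A complete-case figure, √[(1 − own-entry loss)/(1 − paired loss)] − 1, is near an upper bound. At 80% and ρ = 0 it gives √(0.998/0.912) − 1 = 4.6% at Week 12 and √(0.993/0.853) − 1 = 7.9% at Week 24. At 85% the figures are 1.0% and 2.1%.

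**Baseline.** Ten mornings and ten evenings out of 14 leave at least 10 + 10 − 14 = 6 pairs, so an eligible participant loses baseline only at exactly 6 pairs. With independent misses in the same window, the exact multinomial probability given eligibility is 0.8% at 80% and 0.2% at 85%.

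**The case against.** The best case for leaving the rule alone is that it hardly matters. The endpoints are secondary, in a Phase IIa study that sizes none of them. The 80% to 85% range is a trigger for site follow-up, not an expected completion rate. At 90% with independent misses, the standard error rises by at most 0.05% at Week 12 and 0.14% at Week 24. Reasons such as hospitalisation or treatment interruption would remove mornings and evenings together, so the independence columns are probably pessimistic. The short Week 12 window affects only participants with a combined SV5/SV7. The 29.2% figure needs the earliest permitted SV7, and there the own-entry rule still loses 5.0%, so part of that loss comes from window length rather than pairing. A common day-level rule is also simple and treats both arms alike.

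All of this stands as to size, and the rule only bites below seven pairs. None of it supplies a reason for pairing. The rule secures no additional score on either instrument, the documents give no rationale for applying it to them, and the undefined term would need clarifying for the programmer anyway.

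**Conclusion.** The concern holds. As written, the completeness rule can set BCSS and Cough VAS two-week means to missing when the instrument's own data are ample, and nothing is gained in return. The cost is a small loss of precision on two secondary endpoints: about 0.1% to 4.4% in standard error across the 80% and 85% scenarios, less at higher completion, and none if missed sessions coincide. It is largest at the named Week 12 and Week 24 time points when the last visit shortens the window. Baseline loss among eligible participants is rare.

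These sizes rest on assumed completion rates and correlations; the mismatch between the rule and the collection schedule does not. No between-arm bias is shown, and the primary endpoint and sample size are unaffected. The rule should be changed because correcting it is nearly free, not because it threatens the trial's conclusions.

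**What to change.** In SAP Sections 3.3.1.1 and 3.3.3, limit the paired evening-and-morning rule to PEF. For BCSS, require at least 7 non-missing evening scores in the 14-day period; for Cough VAS, at least 7 non-missing morning scores. Apply this at baseline and after baseline, in line with the once-daily rule already given for CompEx variables. Keep the floor of seven own entries where a window is shorter or longer than 14 days, and say what counts as an entry.

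The cost is a short text and derivation change, and the minimum number of scores behind each mean stays at seven. It should be made before unblinding. If that is no longer possible, report the own-entry version as a sensitivity analysis.

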3.3.1.2 Derivations

Absolute change from baseline

Absolute change from baseline will be derived as follows:

Absolute change from baseline = (post-randomisation value – baseline value).

Time since COPD diagnosis (years)

Time from COPD first diagnosis date to randomization will be calculated as (date randomized minus date of first diagnosis of COPD plus one) divided by 365.25. If date of first diagnosis of COPD is partially missing, then imputed date will be used.

Time since COPD symptoms started (years)

Time from COPD first symptoms date to randomization will be calculated as (date randomized minus date of first symptoms of COPD plus one) divided by 365.25. If date of first symptoms of COPD is partially missing then imputed date will be used.

Time since last exacerbation (months)

Time since last COPD exacerbation date to randomization will be calculated as (date randomized minus date of most recent exacerbation plus one) divided by 365.25 and multiplied by 12. If date of first symptoms of COPD is partially missing then imputed date will be used.

Total number of COPD exacerbations within previous 24 months prior to screening This number is derived by counting the number of events occurring prior the screening.

Duration of AECOPD

The start and stop dates of COPD exacerbations will be determined as follows:

The start and stop dates of mild AECOPD will be the onset and resolution of worsened symptoms, respectively.

The start dates of moderate and severe AECOPD will be the earliest of:

- Start date of systemic corticosteroids for AECOPD
- Start date of antibiotics for AECOPD
- Date of hospital admission due to AECOPD

The stop dates of moderate and severe AECOPD will be the latest of:

- End date of systemic corticosteroids for AECOPD
- End date of antibiotics for AECOPD
- Date of hospital discharge due to AECOPD

If less than 7 days have elapsed since the end date of an AECOPD and the start date of a new AECOPD, the second event will be considered a relapse of the prior AECOPD in the statistical analysis.

Time from first IP administration to AE onset (days)

Time from first IP administration to AE onset will be calculated as date of AE onset minus date of first IP administration plus one.

Time from latest IP administration to AE onset (days)

Time from latest IP administration to AE onset will be calculated as date of AE onset minus date of last IP administration plus one.

Time from first IP administration to death (days)

Time from first IP administration to death will be calculated as date of death minus date of first IP administration plus one.

Time from latest IP administration to death (days)

Time from latest IP administration to death will be calculated as date of death minus date of latest IP administration plus one.

Duration of AE (days)

Duration of AE will be calculated as stop date of AE minus start date of AE plus one.

Duration of acute worsening events (days)

Duration of acute worsening events (AWE) will be calculated as stop date of AWE minus start date of AWE plus one. If two or more AWEs overlap then the duration of worsening will be calculated as stop date of latest AWE minus start date of first AWE plus one.

Duration of Interruptions

Duration of interruption will be calculated as the end date of dose interruption minus the start date of dose interruption plus one.

The start date of dose interruption is the day when drug was interrupted and the treatment was not administered.

3.3.1.3 Handling of missing data

No imputation for missing efficacy endpoints will be done.

Missing safety data will generally not be imputed. However, safety assessment values of the form of "< x" (i.e., below the lower limit of quantification) will be imputed as "0.5x LLOQ" in the calculation of summary statistics but displayed as "< x" in the listings. No imputation will be done for laboratory values of the form ">x" (i.e., above the upper limit of quantification) and the value ">x" will be displayed in the listings. Note that 0 should not be used as an imputed value in case the endpoint requires a log transformation.

Additionally, adverse events (AEs) that have missing causality (after data querying) will be assumed to be causally related to study drug.

Plasma concentrations below the lower limit of quantification will be reported as NQ (Not Quantifiable) in the listings with the LLOQ defined in the footnotes of the relevant TFLs. Individual plasma concentrations that are Not Reportable will be reported as NR and those that are missing will be reported as NS (No Sample) in the listings. Plasma concentrations that are NQ, NR or NS will be handled as follows for the provision of descriptive statistics:

- Any values reported as NR or NS will be excluded from the summary tables and corresponding figures.
- At a time point where less than or equal to 50% of the concentration values are NQ, all NQ values will be set to the LLOQ, and all descriptive statistics will be calculated accordingly.
- At a time point where more than 50% (but not all) of the values are NQ, the gmean, gmean ± gSD and gCV% will be set to NC (as Not Calculated). The maximum value will be reported from the individual data, and the minimum and median will be set to NQ.
- If all concentrations are NQ at a time point, no descriptive statistics will be calculated for that time point. The gmean, minimum, median and maximum will be reported as NQ and the gCV% and gmean ± gSD as NC.
- The number of values below LLOQ (n < LLOQ) will be reported for each time point together with the total number of collected values (n).

Three observations > LLOQ are required as a minimum for a plasma concentration to be summarised. Two observations > LLOQ are presented as minimum and maximum with the other summary statistics as NC.

3.3.1.4 Dates Imputation

Imputation of partial missing AE dates

Date and time of AE are mandatory eCRF fields. In the rare cases of missing AE date, following rules will be applied. Completely missing AE dates are not imputed.

Partial missing AE end dates are imputed as below:

- If the AE is ongoing, the end date is stated to missing.
- If the AE is not ongoing, and:
 - o If only the day is missing: Assume the last day of the collected month.
 - o If the month is missing: Assume 31-DEC of the collected year.

After applying these rules, if the imputed AE end date is after the end of study date, set the AE end date to end of study date.

Before proceeding with the AE start date imputation, the AE end date is imputed as described above, if necessary.

Only partial AE start dates are imputed. Dates which are completely missing are not imputed. Partial dates are imputed as described below:

- If the day is missing and:
 - o If the month and year are different from the month and year of the first dose of IP, assume 01-MMM-YYYY.
 - If the month and year are the same as the first dose of IP month and year and the end date is on or after (including ongoing / missing) the first dose of IP, then assume the date of the first dose of IP.
 - o If the month and year are the same as the first dose of IP month and year and the end date is prior to the first dose of IP, then assume the end date.
- If the month is missing and:
 - o If the year is different from the year of first dose of IP, assume 01-JAN-YYYY of the collected year.
 - o If the year is the same as the first dose of IP year and the end date is on or after (including ongoing / missing) the first dose of IP, then assume the date of the first dose of IP.

o If the year is the same as the first dose of IP and the end date is prior to the first dose of IP, then assume the end date.

After applying these rules, if the imputed AE start date is after a complete AE end date then assume the same date as the complete AE end date; if the end date is missing and the imputed AE start date is after the end of study date then assume the same date as the study end date.

Imputation of partial missing medication dates

Both, completely missing and partially missing concomitant medication start dates are not imputed.

Completely missing medication end dates are not imputed. Partial missing concomitant medication end dates are imputed as below:

- If the medication is ongoing, the end date is set to missing.
- If the medication is not ongoing, and:
 - o If only the day is missing: Impute with the last day of the collected month.
 - o If the month is missing: Impute with 31-DEC of the collected year.

In case the medication end date is after the end of study date after applying the above rules, the concomitant medication end date should be set to end of study date.

Imputation of partial missing COPD/Medical history dates

Only partial COPD/medical history dates will be imputed. Dates which are completely missing will not be imputed. Partial start dates will be imputed as described below:

- If only day is missing, then impute the first day of the month.
- If the month is missing, then impute 1st of JAN of the collected year.

Partial end dates will be imputed as described below:

- If only day is missing, then impute the last day of the month.
- If month is missing, then impute 31st DEC of the collected year.

